Assessment of Side Effects and Medication Compliance: The research nurse and psychiatrist will query about side effects related to the study medication. Reported side effects and other treatment emergent events since the past visit will be recorded; additionally, the severity of the side effect/treatment emergent event, the action taken, and the continuation or resolution of the side effect/treatment emergent event will be documented.

You can upload charts or diagrams if any Table 1 inpatient.pdf Table 2 outpatient med dosing.pdf

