#### **Outpatient Study Assessments**

Adverse Effects measures: The Systematic Assessment for Treatment and Emergent Events (SAFTEE; Johnson et al. 2005) adapted for clonazepam will be performed weekly to identify adverse symptoms. Benzodiazepine withdrawal measure: The Clinical Institute Withdrawal Assessment-Benzodiazepines (CIWA-B)(Busto, 1989) is a 22-item scale to assess the degree of benzodiazepine withdrawal. Cannabis Craving measure: The Marijuana Craving Questionnaire (MCQ) is a 47-item instrument (Heishman et al. 2001).

Columbia Suicide Severity Rating Scale: Will be used to monitor suicidality at baseline and twice a month during the study period.

Medical Evaluation and Monitoring: A medical history and physical exam will be performed during screening. Serum pregnancy testing will be performed during screening and urine pregnancy testing will be performed monthly during the study. Complete blood count, electrolyte, urinalysis and liver function tests will be performed during screening and monthly during the study. Height and weight will be measured and baseline body mass index (BMI) calculated during screening. Temperature, pulse, blood pressure, and weight will be measured at every study visit.

Cannabis Use Outcome measures: Cannabis use will be recorded by the timeline followback (TLFB) method (Litten and Allen 1992) modified for cannabis and confirmed by creatinine-normalized quantitative urine THC levels. Other substance (including nicotine and alcohol) use self-report data will also be gathered during the TLFB interview. Urine samples for quantitative urine THC levels and creatinine will be collected under directly-observed conditions during screening and at each study visit (twice weekly). Creatinine levels can be used to control for urine concentration variability and screen for adulterated samples. Creatinine-corrected quantitative urine THC levels will then be used to confirm self-reported cannabis use, using a method similar to that described by Preston et al. (Preston et al. 1997) for cocaine dependence, where an obvious pattern of new use (i.e., level more than doubles in the past two days) overrides a self-report of no use.

Cannabis Withdrawal measure: We will use the 22-item version of the Marijuana Withdrawal Checklist (MWC; Budney et al. 1999) that measures subject-rated severity as the primary outcome measure of withdrawal.

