## **Risks/Discomforts/Inconveniences**

Risks that could be encountered during the study period **Potential Risks** 

There are risks associated with benzodiazepine misuse, withdrawal and overdose. The more severe withdrawal symptoms have usually been limited to those patients who received excessive doses over an extended period of time. Generally milder withdrawal symptoms (e.g., dysphoria and insomnia) have been reported following abrupt discontinuance of benzodiazepines taken continuously at therapeutic levels for several months. Misuse or taking benzodiazepines for long periods of time may lead to a drug habit, where a patient could become dependent on a benzodiazepine, such as clonazepam, to function. Benzodiazepines are commonly misused and have a potential for abuse. They can have harmful effects and are easily available. Death and serious illness rarely result from benzodiazepines, such as clonazepam; however this medication can be dangerous when taken with either alcohol or other medications. The combination of substances can even cause death. The most common adverse reactions noted with clonazepam are: drowsiness, confusion, dizziness, difficulty concentrating and loss of memory. Participants will be cautioned against driving a car or operating machinery, and will be warned against stopping the medication abruptly or drinking alcohol while participating in the study. We will also closely monitor for abuse-related behavior, both in our rating scales and in our weekly clinical visits.

An additional of risk of research participation is cannabis withdrawal, e.g., irritability, anxiety, disruptions in sleep and/or food intake. All participants are fully informed of the side effects that they might experience, and because all currently smoke cannabis, these effects should be familiar to them. Finally, the combination of clonazepam and cannabis may have additive intoxicating effects. The research psychiatrist will discuss misuse, withdrawal, and risks of overdose with each participant.

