Study: # 7343 entitled EFFECT OF CLONAZEPAM ON CANNABIS WITHDRAWAL AND RELAPSE IN TREATMENT-SEEKING PATIENTS: COMBINED INPATIENT/OUTPATIENT STUDY

PI: [name].

NCT# NCT02913924

Statistical Analysis Plan (Grant): 9/19/2013

Amended 4/15/2016 (DSMP)

Grant Submission U54 DA037842: 9/19/2013

3. Data Analysis a. Outcome Measures and Covariates

i. Primary outcome measures: 1) Cannabis use: The time to sustained relapse defined as 5 days of cannabis use over a 7 day period as recorded by the Timeline Followback method and confirmed by creatinine-normalized quantitative urine THC levels, or time to dropout of study, whichever comes first (survival outcome).

ii. Secondary outcome measures: These measures are designed to capture changes in cannabis consumption patterns and other symptoms not measured by the primary outcome measures.

1) Abstinence during the final two weeks (study weeks 11 and 12) of the study (dichotomous)

2) Retention in treatment (survival outcome)

3) Days per week of cannabis use (continuous longitudinal)

4) Cannabis withdrawal: measured by weekly Marijuana Withdrawal Checklist (continuous longitudinal)5) Cannabis craving: measured by weekly Marijuana Craving Questionnaire (continuous longitudinal)

6) Sleep disturbance: measured by the Medical Outcomes Study—Sleep Scale (continuous longitudinal)

iii. Covariates: 1) Demographic characteristics (e.g., gender, age) 2) Baseline severity of cannabis use (measured by the quantity of cannabis per using day at baseline)

iv. Other measures: Adverse effects, as measured by the Systematic Assessment for Treatment and Emergent Events (SAFTEE), will be assessed, including potential effects on compliance and outcome.

b. Sample Size and Randomization: The Research Core will supervise randomization procedures. A total of 72 patients will be recruited over a 2.5-year period and randomized to the double-blind treatment trial, with 36 patients randomized to each of the two treatment groups, nabilone/XR-NTX arm and placebo arm. The randomization sequence will be balanced in blocks of random size (2, 4, 6) to prevent clinicians from guessing what the next patient's treatment might be.

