Hypothesis 5: Over time, subjects in the nabilone and XR-NTX group will experience significant reduction in the pattern of cannabis withdrawal symptoms (measured as mean Marijuana Withdrawal Checklist score per week) compared to the subjects in the placebo group.

Hypothesis 6: Over time, subjects in the nabilone and XR-NTX group will exhibit significantly reduced cannabis cravings (as measured by Marijuana Craving Questionnaire) compared to subjects in the placebo group.

Hypothesis 7: Over time, subjects in the nabilone and XR-NTX group will experience significantly less sleep disturbance (as measured by the Medical Outcomes Study Sleep scale) compared to subjects in the placebo group. To test the secondary hypotheses 5, 6, and 7 we will use the same model as in (3) where Yijt is the appropriate outcome variable (as specified for each hypothesis) for the i th subject in the treatment group j at week t (t =1, 2, ..., 12). We will first test the interaction effect of group and time as described for Hypothesis 4.

iii. Exploratory Analyses We will explore whether there are differences between the two groups with respect to the number of adverse effects, side effects, and tolerability in relation to the primary outcome. We will also explore whether co-occurring psychiatric disorders, gender, concurrent treatment exposure, trauma history, or impulsivity are predictors of treatment outcome.

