A4. Power calculation and sample size Cannabis Withdrawal. We hypothesize that clonazepam will decrease symptoms of cannabis withdrawal (e.g. ,irritability, sleep efficiency). With a sample size of 80, the test of a single contrast at the 0.050 level will have >90% power to detect a 25% decrease in these ratings under conditions of medication administration compared to placebo, assuming the same between-level correlation and SD than our earlier studies. Cannabis Relapse: The time to relapse as recorded by the Timeline Follow Back method and confirmed by creatinine-normalized quantitative urine THC levels, or time to dropout of study, whichever comes first (survival outcome). The sample size of 80 was chosen to ensure sufficient power (at least 80%) of a two-sided test with level of significance 5% for detecting difference between the two experimental treatments with respect to time to relapse, based on the Cox proportional hazards model. We expect that the clonazepam group will have greater time to sustained relapse than the placebo group. The rate of survival for the placebo group can be expected to be 15% based on our prior studies. With 40 per arm, we will be able to detect a difference in proportion of surviving in placebo versus clonazepam of approximately 27% (i.e. 15% on placebo vs 41.81% on clonazepam). This corresponds to a hazard ratio of 0.46 (Machin et al. 1997). The power computation was performed assuming that the covariates (i.e., baseline cannabis

use and age) do not have any predictive power. If they do, the power of the primary hypothesis will be higher than 80%. The 26.81% rate difference is consistent with a medium to large sized effect, which is what we are seeking in this early Phase II trial. This represents an effect that would be clinically meaningful and likely to make a substantial impact on the success of clonazepam treatment in clinical practice. The proposed sample size n=40 for clonazepam group will also enable us to estimate the relapse and retention rates of the treatment group with a 95% confidence interval, $\pm 15.5\%$, in the worst case.

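### The only stated between-arm comparison of adverse effects is an exploratory number, and nothing separates clonazepam's own effects from the cannabis-withdrawal symptoms it is expected to reduce

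*Protocol*

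**What the plan says.** - **Status of safety.** The protocol (Secondary Outcome Measures) and SAP A2 both list side effects and tolerability as a secondary outcome.
- **Instrument.** Under Outpatient Study Assessments, the protocol says the SAFTEE "adapted for clonazepam will be performed weekly to identify adverse symptoms". Table 3 schedules it at Baseline and in each of Weeks 1 to 12. The items of the adapted form are not listed.
- **What is recorded.** Study Procedures (Assessment of Side Effects and Medication Compliance) states: "Reported side effects and other treatment emergent events since the past visit will be recorded". Severity, action taken and outcome are noted for each event.
- **Analysis.** SAP 3.a.iv places the SAFTEE outside its lists of primary and secondary outcomes and says: "Adverse effects, as measured by the Systematic Assessment for Treatment and Emergent Events (SAFTEE), will be assessed, including potential effects on compliance and outcome". No scoring rule follows. SAP 3.e.iii, headed exploratory, will look for "differences between the two groups with respect to the number of adverse effects, side effects, and tolerability in relation to the primary outcome". That text sits in the part of the SAP whose hypotheses name nabilone and XR-NTX. The clonazepam part (A2, A4, C3) gives no analysis of side effects and tolerability.
- **Two kinds of symptom.** Risks/Discomforts/Inconveniences says of the drug: "The most common adverse reactions noted with clonazepam are: drowsiness, confusion, dizziness, difficulty concentrating and loss of memory". It names as a further risk "cannabis withdrawal, e.g., irritability, anxiety, disruptions in sleep and/or food intake".
- **Expected direction.** SAP A4 hypothesises that clonazepam lessens withdrawal symptoms and claims more than 90% "power to detect a 25% decrease in these ratings under conditions of medication administration compared to placebo".

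**The concern.** The two symptom groups are expected to move in opposite directions on clonazepam: its own sedative and cognitive effects up, cannabis-withdrawal symptoms down. Recording is broad, and the patients come straight from near-daily cannabis use. If both groups are recorded and then compared as a number, part of any excess of drug effects is offset by the reduction in withdrawal. The better the drug works on withdrawal, the larger the offset.

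The protocol recognises the distinction elsewhere: its rule for removing deteriorating patients sets aside the discomfort usual in cannabis withdrawal. No matching rule is stated for counting adverse effects.

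At stake is how a null comparison is read. For a controlled sedative given to patients with a substance use disorder, similar numbers in the two arms could be reported as good tolerability when the kinds of effect differ.

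**Working it through.** The plan states no figure for adverse effects, so there is none to reproduce. The steps below ask what a pooled count would show if one were used.

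**Inputs from the documents.** 40 patients per arm and a 25% fall in withdrawal ratings (SAP A4); two-sided 0.05 (SAP C3); five clonazepam terms and four withdrawal terms (Risks/Discomforts/Inconveniences).

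**Assumptions.** The adapted SAFTEE includes withdrawal symptoms; the number is pooled over types; the 25% fall in ratings carries over to event counts; follow-up is equal in both arms. The documents establish none of these.

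**1. Break-even rise.** Let s be the share of placebo-arm events that are withdrawal symptoms (not given) and g the relative rise in clonazepam-type events. The totals are equal when

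0.75s + (1 + g)(1 − s) = 1, so g = 0.25s/(1 − s).

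- s = 20%: 0.05/0.80 = 6%
- s = 50%: 0.125/0.50 = 25%
- s = 67%: 50%
- s = 80%: 0.20/0.20 = 100%
- s = 0: nothing is masked

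**2. A limiting case.** Take s = 80%. Placebo has 4 withdrawal-type and 1 clonazepam-type event per patient; clonazepam has 3 and 2. The totals are 5 and 5, so z = 0 and a test of the total rejects only at its 5% error rate. For the clonazepam-type count alone, with variance φ times the mean,

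z = (2 − 1)/√(φ × 3/40).

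This gives 3.65 at φ = 1 (power 95%) and 2.58 at φ = 2 (power 73%). The 4:1 split is chosen to cancel exactly, so it shows the mechanism and is not a forecast.

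**3. A second model, by item.** Let each of the four withdrawal terms occur in a fraction p of placebo patients and fall by a quarter. This removes 4 × 0.25 × p = p events per patient. The loss is offset when each of the five clonazepam terms rises by p/5 = 0.2p. Simulation (20,000 replicates, 40 per arm, t-test on per-patient counts, independent items, each clonazepam term at an assumed 15% on placebo) gave the power to show an excess on clonazepam:

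| p | Rise per term fully hidden | 10-point rise: pooled / separate | 20-point rise: pooled / separate |
|---|---|---|---|
| 0% | none | 71% / 71% | over 99% / over 99% |
| 20% | 4 points | 20% / 70% | 83% / over 99% |
| 40% | 8 points | 5% / 70% | 51% / over 99% |
| 60% | 12 points | 1% / 70% | 25% / over 99% |

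At p = 60% and a 10-point rise, drug-type effects are 5 × 0.10 = 0.50 per patient higher and withdrawal events 0.60 lower. The pooled mean is therefore 0.10 lower on clonazepam.

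**4. Reading.** Both models agree. The effect is nil if the form holds no withdrawal symptoms, a dilution if it holds few, and a full mask only if they make up much of what is recorded.

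**The case against.** The strongest reply is that the plan never says one total is formed. SAP 3.e.iii lists number, side effects and tolerability, ties them to the primary outcome, and is exploratory. A reader might infer that safety will be judged on a single SAFTEE total in which benefit cancels harm. The documents do not support that: pooling is one reading of a short sentence, the items are not shown, and a form adapted for clonazepam may leave withdrawal symptoms out.

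Other parts of the reply:

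- **The 25%.** It is a detectable fall in ratings, not a predicted fall in SAFTEE events over 12 outpatient weeks. SAP A4 expects only 15% of placebo patients to survive without relapse or dropout, and relapsers stay in the trial, so withdrawal need not dominate later reports. This stands, and it is why the size is given as a range.
- **Other safety evidence.** Three of the five clonazepam terms are cognitive. Cognitive task performance is its own secondary outcome, and SAP C3 analyses task performance and subjective effects. The CIWA-B, the C-SSRS, laboratory tests, vital signs and DSMB review also bear on safety. This stands against any claim that safety rests on the SAFTEE alone. It does not close the gap: outpatient cognitive measures fall at baseline, week 8 (the taper week) and week 12, and dizziness and drowsiness are not task scores. The weekly SAFTEE is the main systematic record of such effects during outpatient dosing.
- **Baseline.** A reader might infer that symptoms present before the first dose are counted as adverse effects. The protocol records treatment-emergent events and schedules a Baseline SAFTEE, so silence in 3.e.iii does not show this. What stands is that no rule is stated.
- **Risk in splitting.** Risks/Discomforts/Inconveniences names dysphoria and insomnia as benzodiazepine-withdrawal symptoms. Filing anxiety or sleep items only with efficacy, or dropping weeks 8 to 12, could hide harm. This stands, and the fix allows for it.

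**Conclusion.** The point holds in a limited form. A secondary outcome has only one stated between-arm comparison, an exploratory number. Nothing in the plan separates clonazepam-type effects from withdrawal symptoms that the drug is expected to reduce, or sets a rule for severity, dosing period or Baseline.

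If the adapted SAFTEE includes withdrawal symptoms and the number is pooled, an excess of drug effects could be diluted or masked. If event counts also fell by 25%, the rise hidden completely would be about 6% at a 20% share of withdrawal events and 25% at a 50% share. If the form omits such symptoms, there is no masking of this kind. The documents do not show that masking will occur. They show that the stated analysis could not rule it out, although the data to do so are already collected. The primary outcomes are unaffected.

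**What to change.** Amend SAP 3.e.iii, before unblinding, so that it applies to clonazepam and states:

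1. **Main comparison.** A between-arm comparison of the clonazepam-type SAFTEE items, taken from the list in Risks/Discomforts/Inconveniences. Count an item when it is new or worse than the patient's own Baseline SAFTEE, during the dosing period (weeks 1 to 7 in the outpatient schedule).
2. **Full tables.** Every SAFTEE item by arm and severity, with the week 8 taper and weeks 9 to 12 shown separately. Flag patients whose taper was extended.
3. **Ambiguous items.** Anxiety, insomnia and dysphoria stay in the safety tables and are also reported with the withdrawal outcomes.
4. **Overall count.** Keep it as a supporting summary.

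The Baseline rule does not replace the split by type. If Baseline is taken while patients still use cannabis (its timing relative to admission is not stated), withdrawal symptoms will themselves be new afterwards.

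The cost is a few SAP sentences, an item list agreed by blinded staff, and a few more exploratory results to report. Baseline and weekly SAFTEE data and event severity are already collected.

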## **Specific Aims and Hypotheses**

#### Specific Aims and Hypotheses

#### Primary Outcome Measure:

(1) Cannabis withdrawal (mood, sleep quality and duration, food intake)

(2) Cannabis relapse defined as (1) time to any MJ use as recorded by the timeline follow back method and

confirmed by urine metabolite levels, or (2) time to dropout, whichever comes first, and (3) medication compliance (% of pills taken) or time to discontinuation. Participants who relapse will continue in the trial to obtain secondary outcome measures.

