#### **Inclusion/Exclusion Criteria**

Name the subject group/sub sample Adults with CUD Create or insert table to describe the inclusion criteria and methods to ascertain them

1) Meets DSM 5 criteria for CUD of at least moderate severity ( $\geq$  4 symptoms) and is seeking treatment for cannabis use. Clinical interviews (telephone, psychologist, physician)

2) Reports using cannabis an average of 5 days per week over the past 4 weeks

Timeline Follow-back procedure modified for marijuana (MJ-TLFB); urinary THC-COOH > 100 ng/mL Legal identification

3) 18-65 years of age

Create or insert table to describe the exclusion criteria and methods to ascertain them

1) Individuals with a lifetime DSM-5 diagnosis of
schizophrenia, schizoaffective disorder, or bipolar disorder

2) Individuals meeting current DSM-5 criteria for any other psychiatric disorder that may, according to the investigator's judgment, require either pharmacological or non-pharmacological intervention over the course of the study

3) Participants taking psychotropic medication

4) Known history of allergy, intolerance or hypersensitivity to benzodiazepines

5) Episodic or chronic use of benzodiazepines

6) Pregnancy, lactation, or failure to use adequate contraceptive methods (condoms, diaphragm, birth control pill, IUD) in female patients who are currently engaging in sexual activity with men.

7) Unstable medical conditions, such as poorly controlled hypertension, which might make participation hazardous

8) Participants with a current DSM-5 diagnosis of an alcohol of substance use disorder (abuse or dependence) other than cannabis or nicotine use disorder

MINI International Neuropsychiatric Interview for DSM V and psychiatric assessment

MINI International Neuropsychiatric Interview for DSM V and psychiatric assessment

Psychiatric assessment Psychiatric assessment, medical history, physical examination, and serum and urine laboratory testing

MINI International Neuropsychiatric Interview for DSM 5 and psychiatric assessment, urine toxicology; urine toxicology

Clinical interview, Medical history, and serum HCG

Medical history, physical examination, electrocardiogram, and serum and urine laboratory testing MINI International Neuropsychiatric Interview for DSM 5 and psychiatric assessment, urine toxicology,

	breathlyzer
9) Are legally mandated to participate in a substance use disorder treatment program	MINI International Neuropsychiatric Interview for DSM 5 and psychiatric assessment

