## **Study Procedures**

Describe the procedures required for this study

*Study Participants*: Participants will be 80 men and nonpregnant women with CUD who report using cannabis a minimum of 5 days per week over the past 28 days. The minimum threshold of a near-daily pattern of cannabis use will select a population with moderate-to-severe CUD. This level of severity is consistent with the sample in our previous clinical trial (Levin et al. 2011), and, we suspect, typical of individuals with CUD who seek treatment. This sample is less likely to achieve abstinence spontaneously or in response to non-medication aspects of the trial (e.g., general therapeutic support), and thereby minimize the placebo response rate. Selecting for near-daily cannabis users will also prevent a "floor effect" (i.e., participants using cannabis infrequently at baseline would be unlikely to demonstrate significant improvement).

**Inpatient phase**: Patients seeking cannabis treatment will move into the inpatient unit at NYSPI for 5 nights. On move-in day, participants will only receive the PM capsule administration; all capsules will be given under observation and will be double blind. During the next 4 days (days 2-5; Table 1), we will measure medication effects on cannabis withdrawal, including measures of mood, cannabis craving,

objective and subjective measures of sleep, and food intake in our Outpatient Marijuana Laboratory. Cannabis relapse measures will begin following discharge on day 6.

**Outpatient phase**: After discharge from the inpatient phase, 12-weeks of outpatient treatment will be conducted (Table 2). Study visits will occur twice weekly. One visit per week will be with the research psychiatrist for a Medical Management session to perform study assessments and to monitor medication effects and compliance. Participants will have a manual-guided (Pettinati et al. 2005) supportive behavioral treatment session with the research psychiatrist each week. This psychosocial intervention facilitates compliance with study medication and other study procedures, promotes abstinence from cannabis and other substances, and encourages mutual-support group attendance. The second visit each week will be for vital sign monitoring, urine toxicology and completion of self-report measures. Participants will be given cash incentives contingent on study visit attendance and completing other study procedures with the objective of achieving a high treatment adherence.

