## Blood and other Biological Samples

Please create or insert a table describing the proposed collection of blood or other biological specimens Approximately 20 ml of blood (4 teaspoons) will be drawn at the time of baseline assessment, weeks 4, 8, and study completion for routine analyses (hematology, blood chemistry (including liver function tests), and blood pregnancy test for women). They may be repeated during the study if clinically indicated. Approximately, 80 ml of blood will be drawn overall (i.e., baseline, weeks 4, 8, and study completion = 4 x 20 ml = 80 ml).

Quantitative urine toxicology screens for THC with Creatinine will be conducted at each visit (2 per week) and serve as an objective marker of current cannabis use.

HIV testing will be offered in order to determine the HIV status of all possible participants; participants may refuse if they do not want to be tested. Nursing staff will provide Pre and Post-test counselling to assist participants with any HIV+ results. Pre-HIV test counselling discusses the possibilities of a HIV+ test and the procedures after a positive HIV test is found. Post-HIV counselling assesses for suicidal and/or homicidal ideation, along with domestic violence issues. If a person tests positive for HIV, the research psychiatrist on staff with be notified and will do a secondary evaluation for necessity of immediate psychiatric care. Additionally the nursing staff will notify the department of health and provide a list of referrals for follow-up care.

A confirmatory HIV test will not routinely be done due to the accuracy of the saliva quick test, however if a participant tests positive using the saliva quick test a confirmatory blood test will immediately be done.

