#### **Compensation and/or Reimbursement**

Will compensation or reimbursement for expenses be offered to subjects? Yes

Please describe and indicate total amount and schedule of payment(s).

Include justification for compensation amounts and indicate if there are bonus payments.

Subject Compensation: Patients will be provided \$50/night for their inpatient phase (\$250 for 5 nights); they will also receive \$10 for travel at each study visit and will receive an additional \$10 each week for returning their medication bottle with any remaining pills. These payments are in addition to progressive cash incentives for study visit attendance (maximum: \$512.50).

Study Visits and Cash Incentives for Attendance: Progressive cash incentives will be provided for study visit attendance and compliance with other study procedures. Starting at \$2.50 for the first study visit, the value of cash incentives for each subsequent consecutive visit is doubled to a maximum of \$25. Failure to attend study appointments, complete study assessments, and provide a urine sample will reset the value of cash incentives back to their initial \$2.50 from which the value can escalate again according to the same schedule. If an individual attends all visits, they could earn \$512.50 in cash. This reinforcement schedule occurs independently from the cash incentives received for bottle return and compensation for travel.

The maximum amount over the 12 weeks you may potentially earn for attending all study visits is \$1072.50. Participants can potentially earn \$250 for the inpatient phase, \$512.50 in weekly cash payments, \$230 in cash for transportation costs, and \$80 in cash for pill bottle returns.

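### The urine override of a denied use is a bare doubling with no minimum level, so if relapse means any use, a chance rise between two very low values counts an abstinent patient as relapsed

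*Protocol*

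**What the plan says.** **The override.** Under Cannabis Use Outcome measures, the protocol confirms timeline follow-back reports with creatinine-corrected urine THC, using a method described as similar to a cited one for cocaine. In that method "an obvious pattern of new use (i.e., level more than doubles in the past two days) overrides a self-report of no use". On creatinine it adds that "Creatinine levels can be used to control for urine concentration variability and screen for adulterated samples". I find no minimum concentration, no rule for values at or below the quantification limit, and no figure for assay or creatinine variation.

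**The endpoint.** The protocol's Specific Aims define relapse as "time to any MJ use as recorded by the timeline follow back method" with urine confirmation, or dropout if earlier. SAP section A2 repeats this. SAP section 3.a.i, written for a nabilone/XR-NTX trial, instead requires 5 days of use within 7. SAP section A4, the clonazepam power text, speaks both of time to relapse and of time to sustained relapse.

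**The schedule.** "Cannabis relapse measures will begin following discharge on day 6". Outpatient visits, each with a urine sample, are twice weekly, with one in week 1 (Table 3). Levels start high, since entry requires "urinary THC-COOH > 100 ng/mL".

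**The concern.** A ratio rule takes no account of how small the two values are. In an abstinent patient the level falls and may then flatten near the bottom of the assay, where a small absolute change can be a large ratio. A rise between two trivial values meets the printed rule as fully as a rise from a moderate level to a high one.

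If any single use is the event, one such rise ends that patient's event-free time, even though the patient is abstinent and says so. Patients who stay abstinent longest give the most comparisons, and few are expected: 40 × 0.15 = 6 on placebo and 40 × 0.4181 = about 17 on clonazepam at the planned rates. False events unrelated to treatment pull the hazard ratio towards 1 and cost power. They do not raise type I error.

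**Working it through.** **1. The plan's own figure.** Inputs from SAP section A4: 40 per arm, 15% v 41.81% surviving, two-sided 5%, at least 80% power.
- HR = ln(0.4181)/ln(0.15) = 0.460 (stated 0.46).
- Freedman events = (1.96 + 0.8416)² × ((1 + HR)/(1 − HR))² = 57.28.
- Mean event share = 1 − (0.15 + 0.4181)/2 = 0.716, so N = 57.28/0.716 = 80.0.

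The stated N of 80 is reproduced. On this formula power is 80.0%, with nothing to spare.

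**2. How many comparisons.** The compensation section gives USD "230 in cash for transportation costs" at USD 10 per visit, so 23 visits. The attendance incentive agrees: 2.50 + 5 + 10 + 20 + 19 × 25 = 512.50, also 23 visits. That makes 22 consecutive pairs. The rule, however, looks back two days. The two gaps in a week sum to about seven days, so at most one can be two days or less. This leaves at most about 11 pairs (one in each of weeks 2 to 12), and none if visits fall 3 and 4 days apart.

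**3. Chance of a false doubling (assumed noise).** Take independent log-normal noise with a given CV in the corrected level, so s = √ln(1 + CV²). For a flat true level, P(doubling) per pair = 1 − Φ(ln 2/(√2 × s)). Within-week pairs share no sample, so over 11 pairs the chance of at least one is 1 − (1 − p)¹¹. The 22-pair and falling-level columns are simulated (100,000 runs).

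| CV | per pair, flat | 11 pairs, flat | 22 pairs, flat | 11 pairs, half-life 10 d | 11 pairs, half-life 3 d |
|---|---|---|---|---|---|
| 15% | 0.05% | 0.6% | 1.1% | <0.1% | about 0% |
| 20% | 0.7% | 7.1% | 13.8% | 1.7% | about 0% |
| 30% | 4.7% | 42% | 68% | 22% | 3.0% |
| 50% | 15% | 83% | 99% | 71% | 38% |

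The documents give neither the CV nor the half-life. The flat columns hold the level flat from discharge, so they are upper cases for each CV.

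**4. Effect on power.** Let f be the share of true survivors falsely relapsed, equal in both arms. Multiply each survival by (1 − f) and recompute. For f = 20%: survival is 12.0% v 33.4%; HR = ln(0.3345)/ln(0.12) = 0.517; events = 80 × (1 − (0.12 + 0.3345)/2) = 61.8; power = Φ(√61.8 × (1 − 0.517)/(1 + 0.517) − 1.96) = 70.8%.

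| f | survival | HR | power (Freedman) |
|---|---|---|---|
| 0 | 15.0% v 41.8% | 0.460 | 80.0% |
| 10% | 13.5% v 37.6% | 0.488 | 75.6% |
| 20% | 12.0% v 33.4% | 0.517 | 70.8% |
| 30% | 10.5% v 29.3% | 0.545 | 65.4% |

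This treats false events as spread over the whole 12 weeks. In log-rank simulations with 40 per arm and false events only in weeks 7 to 12, which fits the mechanism better, the losses are about 2, 4 to 5 and 7 to 8 points instead of 4, 9 and 15.

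**The case against.** **The event definition is not settled.** A reader might infer that one doubling ends survival time in this trial. The documents do not support that as a flat statement. With 5 use days in 7, or sustained relapse, a single doubling is not an event. Even the any-use wording, read literally, needs use recorded by follow-back and then confirmed by urine, which conflicts with an override that acts on urine against a denial. This objection stands. The point is conditional on the any-use definition, although that is the protocol's own and the 5-of-7 definition sits in text written for another treatment.

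**Twenty-two chances is too many.** A reader might count every consecutive pair. The two-day window limits the count to about 11. This stands, and the mismatch between the window and the visits is a defect in itself.

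**The noise is assumed.** A reader might infer that ordinary variation does double low values in these patients. Nothing in the documents shows it. A constant-CV model also gives the same doubling risk at any level, so the table shows how exposed a bare ratio is, not how much a floor would save. Both points stand.

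**The survivors do not carry the whole treatment difference.** The Cox model uses event timing throughout follow-up, which is why late false events cost less. In addition, if the 15% placebo figure comes from studies scored by the same rule, part of the loss is already in it.

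**The cited method may contain a floor.** It may, but the protocol claims only similarity to a method for a different drug and prints the working criterion as a ratio. A reader applying the printed rule would apply no floor.

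**Conclusion.** The concern holds in conditional form. The printed override is a ratio with no minimum level. If any use is the relapse event, a chance doubling between two very low values is enough to score an abstinent patient as relapsed.

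The frequency cannot be settled from the documents. It is negligible if the corrected level has a CV of 15% or less, or if levels are still falling fast, and common if the level is flat and the CV is 30% or more. A loss of 10% to 30% of true survivors would cost between about 2 and 15 points of power, depending on how many are lost and when. At f = 10% the false relapses number about 0.6 placebo and 1.7 clonazepam patients. The bias is towards no effect, provided that false doublings are unrelated to treatment.

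The change is worth making because the present rule is safe only if the noise is small, and the plan does not show that it is.

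**What to change.** 1. Reconcile the relapse definition across the protocol's Specific Aims and SAP sections 3.a.i, A2 and A4. Say whether a urine override alone can create an event.
2. In Cannabis Use Outcome measures, let urine override a denial only when the level more than doubles **and** the later sample exceeds a creatinine-normalised floor fixed before unblinding, for example one tied to the assay's quantification limit.
3. State which sample pairs are compared, since a two-day look-back does not match twice-weekly visits.
4. Repeat the primary analysis with cannabis use taken from self-report alone, as a sensitivity analysis.

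A floor is preferable to confirmation by the next sample. If a pair begins with a chance-low value, the next sample is also likely to be more than twice that value. In a check with assumed additive noise near the bottom of the assay, a floor removed almost all false doublings, while next-sample confirmation left many.

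The cost is protocol and SAP wording, applied to samples already collected. The downside is that very light use that is denied and stays below the floor will be missed.
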